Treatment comparisons: Discussions with clinicians have indicated expressing results on a linear scale (PDC differences), as opposed to odds ratios or risk ratios, will be most appropriate for interpretation. This occurs naturally with the linear specification in 3.1.a and identity link in GEE. Estimation and inference will be carried out using the parameter estimates from the robust GEE estimation to construct expected PDC treatment differences. The estimand comparisons will be 12-month PDC, calculated by summing the 12 monthly longitudinal parameters, which incorporate the adjustments for early termination of some subjects using the weighted GEE approach. Primary hypotheses involve pairwise comparisons between each of the four study arms, and will be conducted using a multistage gatekeeper approach to account for the multiple treatment comparisons. In stage 1 of this approach, each of the three active intervention arms is compared with the control arm using significance level 0.05/3. In stage 2, if any of the three stage 1 tests is significant, the three pairwise comparisons among active intervention arms are tested with the Holm method using significance level (R/3)*(0.05/3), where R is the number of stage 1 tests that were significant (Dmetrienko et al., 2008).

3.1.b Defining composite PDC for multiple medications

There are 13 CV medication classes considered in this study, and the primary outcome is composite PDC across medications a patient is prescribed. There are several considerations in defining composite PDC, including which of a patient's medications to include in the composite PDC calculation, and calculation of composite PDC with differing lengths of follow-up for different medications.

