We will consider several alternate analyses for medication adherence.

Alternate definitions of PDC: Alternate definitions PDC2 and PDC3 and alternate composite PDC-C2 defined above will be analyzed using the same methods as for the primary definition PDC1-C1. These analyses will provide a better understanding of indirect effects of treatments, and of effects of treatments on all medications a patient is prescribed.

Sensitivity to inactive medications: Among medications gapping at baseline, we will repeat the primary analysis limiting our analyses to those medications that had at least one fill during the follow-up period. This will allow us to assess treatment effects among medications that are known to be active, removing medications that were cancelled but not indicated as such by the medical record.

Medication-specific adherence: We will calculate and analyze PDC for each medication individually, to allow analyses of heterogeneity of treatment effect (HTE) by drug class. Multiple comparisons will be adjusted for separately for each analysis using the gatekeeper approach described above.

Medication gaps: We will consider alternate ways of describing medication adherence behavior, including length of initial gap, time to subsequent gap, average length of gaps, and number of 7-day gaps.

3.1.e Secondary examinations of medication adherence

In secondary analyses we will examine several other questions related to medication adherence, including:

Predictors of medication gaps: We will examine predictors of patients having an initial gap of at least 7 days, using the initial pool of candidate patients, to identify types of patients or prescription characteristics for patients at highest risk for non-adherence. We will also examine predictors of subjects having a gap of at least 7 days while enrolled in the study.

Mechanism of treatment effects: We will carry out analyses examining mechanisms or mediators of treatment effect by considering direct responses to reminders, including time from first reminder to refill, and measures of patient engagement, e.g. number of patient text responses to reminders (intensive text and chatbot arms only).

Heterogeneity of treatment effect: We will carry out analyses examining HTE, specifically i) HTE between the three health care systems, and ii) HTE for patient characteristics or subgroups

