of particular interest. HTE analyses will be carried out using interactions as recommended in Kent et al., 2010 ²³ and will be considered exploratory.

3.1.f Original power analysis

We first estimate sample size required to achieve 80% power for the desired change in the primary outcome, then used current data to show we will be able to achieve this sample size.

Power and sample size: Required sample size was estimated for the primary outcome PDC during the 12 months following randomization. Preliminary data from the VA were used for these estimates. We made the following assumptions: a) Significance using two-sided level 0.05 tests, b) Power at least 80%; c) Difference between treatments in PDC of 10 percentage points; d) Bonferroni adjustment for the 6 pairwise comparisons among the 4 study arms, resulting in adjusted level 0.05/6 (a conservative alternative of the sequential gatekeeper approach to be used in the final analysis as described above, to simplify the calculation of power); e) Analysis stratified by health care system; and f) Within-system and within-treatment residual standard deviation of 12 month PDC equal to 0.22 (mean 0.732), obtained by analysis of 2,859 veterans during the period 01/01/2017 – 12/31/2017 who were prescribed the medications of interest in this study. The large SD is due to a highly left-skewed PDC distribution. (We base sample size estimation on t-tests rather than the proposed binomial models since we do not have estimates of quantities needed to carry out power simulations. We may be able to obtain data for the PDC outcome for a set of baseline patients, in which case we will consider a refined power analysis.) Using these assumptions and estimates, and comparing any two treatments using a linear model with the above residual standard deviation of PDC, we estimate using sample size functions in R that we will need N=119 subjects per treatment arm, total across the three health care systems, for a total of 476 subjects to be randomized across the three health care systems.

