Available sample sizes: We obtained data from each of the three health care systems on the number of patients at the seventeen specific clinics (VA, 4 clinics; UCHealth, 5 clinics; DH 8 clinics) to be included in this study. Figure 1, which we believe to present conservative estimates of enrollment, shows estimated numbers of patients with CVD conditions and prescribed CVD medications across the 3 HCS. Patients will be sent a letter with the opportunity to opt-out. In addition, care providers will be provided lists of their patients who are potentially eligible for the study to see if there are patients that they feel should not be included in the study. Assuming that 75% of patients have a gap, another 15% of patients opt-out of the study following randomization, and 10% of patients do not have usable outcome data, we expect to have usable outcome data for about 7,740 patients across the four study arms.

Planned enrollment: In the patient accrual proposal sent to NHLBI (March 20, 2019), we proposed to enroll 5,000 patients which is a conservative estimate in case the number of patients opting out is higher than in the pilot or the number of patients with 7-day gaps is lower than estimated. Even with this conservative estimate, we expect to have ample subjects (nearly ten times as many as needed) to achieve the necessary power for the primary analysis of PDC. Additional subjects will provide power for secondary analyses, and for analyses of secondary outcomes.

Achieved sample sizes 3/2023

We surpassed our overall enrollment goal of 5,000 patients, enrolling 1,235 patients the VA, 7,266 patients at Denver Health, and 1,000 patients at UCHealth.

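### The stage 2 Holm level can be read two ways that differ threefold, and 0.05/6 is not a conservative stand-in for active-versus-active comparisons when R=1

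*Combined protocol and SAP*

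**What the plan says.** SAP section 3.1.a (Treatment comparisons) treats all six contrasts as primary: "Primary hypotheses involve pairwise comparisons between each of the four study arms". In stage 1, "each of the three active intervention arms is compared with the control arm using significance level 0.05/3". If at least one of these tests is significant, stage 2 opens and the three contrasts among the active arms are "tested with the Holm method using significance level (R/3)*(0.05/3), where R is the number of stage 1 tests that were significant". A methods paper is cited for the procedure, but the ordered cut-offs are not written out. Section 3.1.d applies the same rule to the medication-specific analyses: "Multiple comparisons will be adjusted for separately for each analysis using the gatekeeper approach described above".

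Section 3.1.f sizes the trial at level 0.05/6. It describes that level as "a conservative alternative of the sequential gatekeeper approach to be used in the final analysis as described above, to simplify the calculation of power" and arrives at 119 patients per arm for "comparing any two treatments using a linear model with the above residual standard deviation of PDC".

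**The concern.** Holm's procedure needs one familywise level F. It compares the smallest of three p-values with F/3, the next with F/2 and the largest with F, stopping at the first failure. The stage 2 expression could be F itself (reading A) or the first cut-off F/3 (reading B). In the stage 1 sentence the level is a per-test cut-off. Attached to a named procedure, it would normally be the familywise level. The wording therefore supports both readings, and nothing else in the documents settles the matter.

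The three active-arm contrasts ask whether a behavioural nudge or the chatbot improves on a generic reminder. They are primary, so two analysts following the same text could report different primary conclusions. If the choice is made after results are seen, a conclusion could depend on it.

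The power section has a separate fault. Its conservatism remark covers any two treatments, active-versus-active included, and for those contrasts it does not always hold.

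**Working it through.** **Inputs.** From SAP 3.1.f: "Significance using two-sided level 0.05 tests", 80% power, a difference of 0.10 in PDC, SD 0.22, level 0.05/6 = 0.00833. From 3.1.a: the stage 1 and stage 2 levels. Enrolment from the achieved sample sizes paragraph: "enrolling 1,235 patients the VA, 7,266 patients at Denver Health, and 1,000 patients at UCHealth", so 1,235 + 7,266 + 1,000 = 9,501, or about 2,375 per arm with equal allocation.

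**1. The plan's own figure.** Normal approximation: n = 2(SD/δ)²(z + 0.842)² = 2(0.22/0.10)²(2.638 + 0.842)² = 117.2, so 118. The two-sample t calculation gives 118.97, so 119. The stated N reproduces.

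**2. Cut-offs under the two readings.** R rejections at 0.05/3 release R × 0.05/3 = (R/3) × 0.05 to stage 2. Reading A sets F = (R/3)(0.05/3), one third of what was released. Reading B sets F/3 = (R/3)(0.05/3), so F = (R/3)(0.05), all of it.

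| R | A: steps 1 / 2 / 3 | B: steps 1 / 2 / 3 |
|---|---|---|
| 1 | 0.00185 / 0.00278 / 0.00556 | 0.00556 / 0.00833 / 0.01667 |
| 2 | 0.00370 / 0.00556 / 0.01111 | 0.01111 / 0.01667 / 0.03333 |
| 3 | 0.00556 / 0.00833 / 0.01667 | 0.01667 / 0.02500 / 0.05000 |

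The ratio is exactly 3 in every cell.

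**3. Is 0.05/6 conservative?** For active versus control, yes: 0.01667 > 0.00833. For active versus active at R=1, the first cut-off is 0.00185 (A) or 0.00556 (B), both below 0.00833. Under B only that first step is stricter; step 2 equals 0.05/6 and step 3 exceeds it. Under A the first cut-off is below 0.00833 for every R.

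**4. Power at N=119 (δ = 0.10, SD 0.22, two-sample t).** At 0.05/6 it is 80.0%; for stage 1 at 0.05/3 it is 86.2%. At the first stage 2 step:

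| R | A | B |
|---|---|---|
| 1 | 64.0% | 75.9% |
| 2 | 71.7% | 82.7% |
| 3 | 75.9% | 86.2% |

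Reaching 80% at the R=1 first cut-off takes 154 (A) or 129 (B) per arm. Simulating the full procedure (400,000 replicates, normal outcomes) with one arm effective by 10 points, power for that arm against another active arm is 64% (A) or 73–74% (B). With two arms effective, power for each true active-arm difference is 71–72% (A) or 81% (B). The small ranges reflect pooled versus known variance.

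**5. Power at the enrolled size (2,375 per arm, SD 0.22, all patients usable).** The difference detectable with 80% power at the first step is SD√(2/n)(z + 0.842), where 0.22√(2/2,375) = 0.00638.

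- R=3: A 0.00638(2.773 + 0.842) = 2.31 points; B 0.00638(2.394 + 0.842) = 2.07 points.
- R=1: A 2.52 points; B 2.31 points.
- With the protocol's SD of 0.247: 2.59 (A) and 2.32 (B) at R=3; 2.83 (A) and 2.59 (B) at R=1.

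At R=3 the ratio of sample sizes for equal first-step power is ((2.773 + 0.842)/(2.394 + 0.842))² = 1.25. Full-procedure simulation, with effects as points above control in the three active arms, gives power for each true active-arm difference:

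| Effects | A | B |
|---|---|---|
| +7, +5, +5 | 67% | 80% |
| +2, 0, 0 | 48% | 59% |

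**6. Familywise error.** Suppose k of the stage 1 nulls are true. A false stage 1 rejection has probability at most k × 0.05/3. Without one, R is at most 3 − k, so Holm under B runs at no more than (3 − k) × 0.05/3. The sum is at most 0.05. Simulation agrees: 4.4% under the global null for both readings. With three equal, clearly effective arms it is 4.4% (B) against 1.5% (A). The highest value found was 4.98% (B) against 1.66% (A), for effects +15, +5, +5 at 2,375 per arm.

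**The case against.** The strongest reply is that a level attached to a named procedure is by convention that procedure's own level, so reading A is the default. It is valid and merely cautious, and the cited methods paper may settle how alpha passes to stage 2. On this view, asking for reading B expresses a preference for power and chooses the more lenient threshold. The convention is real, and that B was intended is an inference from the released alpha, not something the SAP states. But the convention does not rescue the section: under A the plan uses a third of the alpha it released, and the conservatism remark in 3.1.f then fails at the first step for every R. A primary decision rule should also be readable from the SAP itself.

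The enrolled-size powers are illustrative. The SAP plans for 10 points, not 2, and the SD comes from veterans while most enrolled patients are at Denver Health. Section 3.1.f itself allows for 10% without usable data. At 2,138 per arm (0.9 × 2,375) the figures become 61% (A) against 75% (B) for +7, +5, +5, and 41% against 52% for +2, 0, 0. The levels fall but the gap between readings remains.

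Finally, the 3.1.f remark sits in a power section that enrolment has overtaken: 9,501 is about twenty times 476. That makes it minor in consequence, but the stated property is still incorrect.

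**Conclusion.** Both points hold. The stage 2 rule is open to two readings that differ threefold at every cut-off of three primary tests. Neither inflates type I error. The cost of the stricter reading is about 11 to 13 percentage points of power for 2-point differences between active arms at the enrolled size, given SD 0.22 and all patients usable. For the planned 10-point difference power is near 100% on both readings, so adequacy of the sample is not in question. What is at stake is whether small differences between active arms are declared significant.

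The statement that 0.05/6 is conservative is right for the three comparisons with control and wrong for active-versus-active comparisons at the first step when R=1, on either reading. At R=2 and R=3 it fails at the first step only under reading A. At N=119 with one effective arm, power for the active-arm contrasts is 64% or 73–74%, not 80%. This should be corrected, though it does not threaten the validity of the trial.

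**What to change.** Before treatment-coded outcomes are examined, write in section 3.1.a that stage 2 applies Holm at familywise level (R/3)*0.05. The smallest p-value is compared with (R/3)*0.05/3, the next with (R/3)*0.05/2 and the largest with (R/3)*0.05, stopping at the first non-significant comparison. This uses all the alpha released by stage 1, is at least as powerful as reading A in every case, and keeps familywise error within 0.05. If the sponsor does intend reading A, that is also valid, but its cut-offs should be listed in the same way. The cross-reference in 3.1.d then inherits a definite rule.

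In section 3.1.f, limit both the conservatism remark and the 80% power at N=119 to the three comparisons with control. Give stage 2 power by R: under the proposed rule, 76%, 83% and 86% at the first step for R = 1, 2 and 3, and about 73–74% through the full procedure when only one arm is effective.

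The cost is a few sentences of SAP text. Sample size, data collection and the primary outcome are unchanged.

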Medications to include in composite PDC: We have considered three ways of selecting medications to include in the primary PDC outcome: PDC1) all medications on which a patient gapped at baseline, PDC2) all medications a patient ever gaps on, calculating PDC from the time of gap, and PDC3) all medications a patient was prescribed at baseline. Medications prescribed after the baseline gap and enrollment will not be included in any of these definitions of PDC, though they will be considered in secondary analyses. Each definition (1-3) has benefits and shortcomings. PDC1 is closest to a pure effect of the intervention, but exploratory analyses of pilot data have shown that many patients who gap in a medication and are randomized also gap in another medication shortly thereafter. Specifically, preliminary data indicate that ~16% of patients gap on an additional medication within 30 days of baseline and ~37% within 90 days. PDC1 will omit these other medications prescribed but not gapped on at baseline. PDC2 provides a similar estimate incorporating these later-gapped medications but excludes medications the patient may never gap on due to reminders for other medications. PDC3 provides an estimate of the overall effect of the interventions on medication patterns, incorporating indirect effects of reminders, but risks inflating PDC and diluting intervention effects by including medications the patient never gaps on. Our primary analyses will use PDC1, while PDC2 and PDC3 will be considered in secondary analyses.

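### PDC2 lets gaps after randomization decide which extra medications count and from when, so its arm differences are a poor guide to indirect effects

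*Combined protocol and SAP*

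**What the plan says.** SAP section 3.1.b considers three medication sets for the composite. The narrowest is settled by the gaps that brought the patient into the trial: "PDC1) all medications on which a patient gapped at baseline". The set at issue here is wider and carries its own starting rule: "PDC2) all medications a patient ever gaps on, calculating PDC from the time of gap". PDC3 takes every medication on the patient's list at entry, gapped or not. Medications first prescribed after enrolment are left out of all three. The ranking is explicit: "Our primary analyses will use PDC1, while PDC2 and PDC3 will be considered in secondary analyses".

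The reason given for looking beyond PDC1 is that, in preliminary data, about "16% of patients gap on an additional medication within 30 days of baseline and ~37% within 90 days". Section 3.1.b then says "PDC2 provides a similar estimate incorporating these later-gapped medications", and adds as a shortcoming that it "excludes medications the patient may never gap on due to reminders for other medications".

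Section 3.1.d applies the primary methods to PDC2, PDC3 and the alternate composite PDC-C2, and says of them jointly: "These analyses will provide a better understanding of indirect effects of treatments". Those methods are the weighted GEE and the pairwise arm contrasts of section 3.1.a.

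Two facts in SAP section 1 matter here. A 7-day gap is the condition for entry, so every randomized patient has at least one baseline-gapped medication. Patients in the active arms are also texted at any later gap on a study medication.

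**The concern.** PDC2 is the PDC1 set plus medications that were prescribed at baseline and gap later. The first part is fixed before randomization. The second part is not: a medication enters when the patient fails to refill it on time, and its clock starts there. Refill behaviour after randomization is what the texts are meant to change.

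If reminders about one medication prevent a gap on another, the spared medication stays out of PDC2 in the texted arm, while its counterpart under usual care gaps and is counted. The two arms are then averaged over different medications and different windows. The success itself (the gap that did not happen) is not scored. An analyst who looks to PDC2 for spillover could therefore see a diluted effect, no effect or, in some circumstances, apparent harm.

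The planned weights do not deal with this. Under section 3.1.a they model whether a monthly value was observed. Because the baseline-gapped medication supplies a value in any case, the selection happens inside the composite, medication by medication.

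**Working it through.** **Plan's own figures.** The SAP gives no figure for PDC2. The nearest is the sample size in section 3.1.f (difference 0.10, SD 0.22, level 0.05/6, power 80%). A two-sample t-test gives 118.97, so the stated 119 per arm is reproduced. The SD of 0.22 is borrowed below; it is not an SD for PDC2.

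**Model A: hazard of a later gap.** Each patient has one baseline-gapped and one other baseline medication.

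- From the SAP: 37% gap by 90 days, so h = −ln(0.63)/90 = 0.00513 per day. This implies 14% by 30 days (SAP about 16%) and 85% by 365 days.
- Assumed: half of the other medications are easy (coverage 0.80 after a gap) and half hard (0.55), average 0.675; coverage before a gap is 0.97; the baseline medication averages 0.671 in both arms, so there is no direct effect.
- Mean time before a gap within the year is 0.846/0.00513 ≈ 164.9 days, leaving 200.1 days after it.

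*Hand check of the extreme case, in which reminders prevent every gap on easy medications:*

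- PDC3. Other medication, usual care: (164.9 × 0.97 + 200.1 × 0.675)/365 = 0.808. Texted: half at 0.97 and half at (164.9 × 0.97 + 200.1 × 0.55)/365 = 0.740, mean 0.855. The difference is +0.047. It is halved because the baseline medication carries equal days: **+0.023**.
- PDC2. A medication with d days after its gap has weight w = d/(365 + d). Averaging (365 − t)/(730 − t) over the gap-time density h·exp(−ht), with zero weight if no gap occurs, gives 0.317. Usual care: 0.671 + 0.317 × (0.675 − 0.671) = 0.672. Texted: 0.671 + 0.5 × 0.317 × (0.55 − 0.671) = 0.652. Difference **−0.020**; simulation gave −0.021.

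*Simulation over the range, with a refill lag of 0 or 20 days after each later gap:*

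| Scenario | PDC3 | PDC2 |
|---|---|---|
| Gap hazard cut 25–50% at random, no direct effect | +0.012 to +0.034 | about 0.000 to +0.005 |
| Same overall cut, all on easy medications, no direct effect | +0.008 to +0.032 | −0.004 to −0.021 |
| As above, with +0.03 on coverage after a gap (PDC1 +0.028) | +0.029 to +0.050 | +0.008 to +0.024 |

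Computed month by month, the second row's PDC2 range is −0.004 to −0.018.

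*Chance of a significant result.* Enrolment is 1,235 + 7,266 + 1,000 = 9,501, or about 2,375 per arm. SE = 0.22 × √(2/2,375) = 0.0064. At level 0.05/3, a spurious −0.007 would be declared significant about 10% of the time, −0.018 about 67% and −0.021 about 81%.

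**Model B: refill lateness.** Fills are 30 or 90 days. Lateness is exponential, with gamma-distributed patient means (mean 12 days, shape 1 assumed), and a gap is lateness of at least 7 days. Each patient has one baseline-gapped and one other medication, pooled as in PDC-C1 over the year. About half of the other medications gap by 90 days under usual care, which is above the SAP's 37%.

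| Reminder effect | PDC3 (pp) | PDC2 (pp) |
|---|---|---|
| Other medication only, lateness halved if patient mean < 15 days | +1.6 | +0.8 |
| Other medication only, lateness halved if patient mean < 10 days | +1.0 | +0.4 |
| Other medication only, all lateness cut 20% | +1.22 | +1.01 |
| Both medications, same three rules in order | +3.4, +2.0, +2.6 | +3.5, +2.1, +2.7 |

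Repeat runs of the first row varied by about 0.1 pp (one gave +1.73 and +0.95). The first two rows give the summary of about +0.4 to +0.9 pp on PDC2 against +1.0 to +1.6 pp on PDC3.

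**The case against.** The case for the plan is strong. PDC2 is secondary. Section 3.1.b names this very exclusion as a shortcoming and credits PDC3 with capturing indirect effects. The sentence in 3.1.d about indirect effects covers PDC2, PDC3 and PDC-C2 together, so it need not lean on PDC2. Section 3.1.d also plans time to subsequent gap and number of 7-day gaps, which measure prevented gaps directly. If reminders act alike on all medications, Model B shows almost no bias.

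All of this stands, and it limits the point to one of interpretation. What remains is that the disclosure concerns which medications are covered. It does not say that the sets and windows can differ by arm. PDC2 is still called similar to PDC1 and still tested by the same contrasts.

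A reader might infer that PDC2 contains only medications that gap after randomization. It does not: "ever" takes in the baseline-gapped medications, and these dampen the bias considerably. In Model A the later-gapped part alone moves by −0.028 to −0.125 in the second scenario, against −0.004 to −0.021 for the full composite.

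A reader might also infer that the comparison is no longer randomized at all. No patient is excluded, each is scored by the same rule, and if reminders do nothing PDC2 has the same distribution in every arm. The difficulty is what a non-null difference means.

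**Conclusion.** The concern holds as a matter of interpretation in a secondary analysis. The later-gapped part of PDC2 is selected and timed by an event that treatment can alter, so an arm difference in PDC2 cannot be read as an indirect effect.

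The usual consequence is attenuation. On the full composite a pure spillover benefit fell to roughly half in Model B (about +0.4 to +0.9 pp against +1.0 to +1.6 pp on PDC3) and nearly vanished in Model A under random prevention. Reversal of sign appeared only when prevention was concentrated in easier medications with no direct effect. Even concentration among better-adhering patients in Model B did not produce it. It would be wrong to conclude that PDC2 will show harm, or that its direction of error is known.

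These sizes rest on assumed coverage, lateness and prevention patterns that the documents do not give. They also use a per-patient gap rate whose denominator is not stated as if it applied to one medication. The primary PDC1 and the secondary PDC3 use sets fixed before randomization and are unaffected.

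**What to change.** In section 3.1.d, report PDC2 descriptively by arm, with no treatment tests and no causal wording. In section 3.1.b, add a sentence saying that its later-gapped medications and their start dates arise after randomization and can differ by arm.

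Base conclusions about indirect effects on PDC3, on the gap outcomes already planned, and on one added outcome: PDC from randomization over medications prescribed at baseline but not gapped then. That set is the PDC3 medications without the PDC1 medications, and it is fixed before treatment in every arm.

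The cost is a few lines of SAP text and one derived variable from data already assembled for PDC3. There are two drawbacks. Medications that never gap dilute the effect, which the SAP already accepts for PDC3. Patients with no such medication at baseline do not contribute; because that restriction is fixed before randomization, it narrows the population without biasing the arm comparison. If outcomes have already been examined by arm, the added outcome should be labelled post hoc.
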